2. LIST OF ABBREVIATIONS

The following abbreviations are used in this study protocol.

Abbreviation Explanation

ACR American College of Rheumatology

AE adverse event

ALT alanine aminotransferase ANCOVA analysis of covariance

AP anteroposterior

AST aspartate aminotransferase

BMI body mass index COX cyclooxygenase

CBC complete blood count

CGIC Clinical Global Impression of Change

CFR Code of Federal Regulations

DF diclofenac

eCRF electronic case report form

FDA Food and Drug Administration

FTA femoral-tibial angle
GCP Good Clinical Practice

GEE generalized estimating equations
HA hyaluronate or hyaluronic acid

IA intra-articular

ICH International Conference on Harmonisation

IRB institutional review board

ITT intention-to-treat K-L Kellgren-Lawrence

Medical Dictionary for Regulatory Activities

MRI Magnetic Resonance Imaging

NRS Numeric Rating Scale

NSAID nonsteroidal anti-inflammatory drug

OA osteoarthritis

OMERACT-OARSI Outcome Measures in Rheumatology - Osteoarthritis Research

Society International

PASE Physical Activity Scale for the Elderly
PGIC Patient Global Impression of Change

PP per-protocol

Seikagaku Corporation Protocol v3.0 613/1121 01-September-2017

SAE serious adverse event

SAR suspected adverse reaction

SF-36 36-Item Short Form Health Survey (SF-36)

SKK Seikagaku Corporation

SOP standard operating procedure

ULN upper limit of normal

US United States

VAS visual analogue scale

WOMAC Western Ontario and McMaster Universities Osteoarthritis Index

3. INTRODUCTION

3.1. Background

Osteoarthritis (OA) is by far the most common joint disorder in the United States (US) and throughout the world, and it is one of the leading causes of disability in the elderly. Osteoarthritis is characterized by damage to joint structures such as hyaline cartilage and subchondral bone, and increases in prevalence with age. Primary symptoms include joint pain and impairment of physical function. The main clinical features are bony swelling, joint effusion, limitation of range of motion, malalignment, and deformation. Treatment for OA aims to relieve pain and improve function. Main treatment options for knee OA are conservative therapies such as exercise, physical therapy, and pharmacotherapy. Pharmacotherapy includes use of oral or topical agents, such as acetaminophen or nonsteroidal anti-inflammatory drugs (NSAIDs), or intra-articular (IA) injections such as hyaluronic acid (HA) or corticosteroids. Surgery is an option for patients when conservative therapy fails to improve symptoms and joint destruction progresses.

Oral NSAIDs are among the most commonly used medications for mild or moderate knee OA pain. Nonsteroidal anti-inflammatory drugs have a fast-acting analgesic and anti-inflammatory effect and are considered to be effective for improving OA symptoms, but individual patient response varies widely. An increase in upper gastrointestinal tract disorders has been reported in patients on long-term use.³ In the 1990s, numerous selective cyclooxygenase (COX)-2 inhibitors were developed to reduce upper gastrointestinal tract disorders, but most of them were withdrawn from the market or their development was halted by 2004 due to concerns about cardiovascular adverse reactions.⁴ The same concerns with selective COX 2 inhibitors have also been reported with oral NSAIDs.⁵

Intra-articular injection therapies also play an important role in the conservative therapy of knee OA. Corticosteroids and HA formulations are typical examples. Corticosteroids have strong anti-inflammatory effects and are given by IA knee injection to patients with moderate to severe knee OA. However, it is generally recommended that corticosteroid injections be limited to 3 or 4 times per year in most cases because of concern over potential progressive joint destruction through repeated injections into the knee joint.⁶ Although the mechanisms of action of IA HA injections are not fully understood, an array of research suggests that HA exerts anti-inflammatory, analgesic, and possibly chondroprotective effects on the joint cartilage.⁷ Due to their viscoelastic properties, IA HA injections also function as a lubricant and a shock absorber. As a result of these effects, IA HA injections exert long-lasting pain relief for some patients with OA of the knee.⁸

Seikagaku Corporation (SKK) has developed and evaluated various HA derivatives that are chemically linked with various NSAIDs and possess the advantages of both IA HA injections and NSAIDs. SI-613, an HA derivative chemically linked with diclofenac (DF), was identified through a series of animal arthritis model studies. As the result of data obtained from the nonclinical studies, a single IA injection of SI-613 is expected to provide analgesic effect for OA pain and to remain in joint tissues for a prolonged period of time to provide potent, sustained analgesia, and could be a highly effective and safe treatment for OA pain.

A phase 1 clinical study performed in healthy Caucasian and Japanese male subjects showed that single IA knee injections of SI-613 were safe and well tolerated. A phase 2 study in 121 Japanese subjects with knee OA was then conducted to explore the efficacy and safety of single IA knee injections of 15 mg SI-613 drug solution, 30 mg SI-613 drug solution, and placebo. SI-613 was well tolerated, resulting in no major safety signals. While the differences between treatment groups for the primary efficacy measurement, the Western Ontario and McMaster Universities Osteoarthritis Index (WOMAC) pain subscore, were not statistically significant, significant improvement compared with

placebo treatment was found for SI-613 treatment for some individual questions in WOMAC stiffness and WOMAC physical function subscores, which were secondary efficacy measurements. Also, the number of individual WOMAC questions with significant improvements for SI-613 over placebo was larger for the 30 mg SI-613-treated group than for the 15 mg SI-613-treated group. After a single IA injection of SI-613 drug solution or placebo, the estimated difference between the SI-613 and placebo groups in the WOMAC subscores tended to be larger for 30 mg SI-613 treatment than for 15 mg SI-613 treatment from Weeks 1 through 8.

A second phase 2 study in 176 Japanese subjects with knee OA was then conducted to explore the efficacy and safety of repeated IA knee injections (1 injection every 4 weeks, total of 3 injections) of 30 mg SI-613 drug solution and placebo. The repeated IA injections of 30 mg SI-613 drug solution showed significantly greater improvements than placebo in the primary endpoints of the WOMAC pain subscore and the subject daily pain score during Week 1 through Week 12. As in the prior study, SI-613 was well tolerated, resulting in no major safety signals.

Based on these results, SKK begins the US clinical program with this phase 2 study, which is designed to evaluate the efficacy and safety of repeated IA injections (1 injection every 4 weeks, with a total of 3 injections) of 30 mg SI-613 drug solution compared with placebo in subjects with symptomatic knee OA.

3.2. Risks and Benefits

For summary of the known and potential risks and benefits to human subjects, please see Sections 6.3 of the SI-613 Investigator's Brochure.

[figure not shown]
3.3. Rationale for Route of Administration, Dosage, and Dosing Regimen

3.3.1. Route of Administration and Rationale

The route of administration of SI-613 is via IA injection into the knee joint.

Intra-articular injection is a common route of administration in medical practice, with many similar injectable HA medical devices approved in the US for the treatment of OA knee pain. Intra-articular injection makes it possible to place SI-613 drug substance directly into the joint cavity without diffusing it into other tissues, which contributes to low systemic exposure.

3.3.2. Dosage and Rationale

The dosage to be used for this study is 30 mg. In the single-dose phase 2 study in Japanese patients with knee OA, it was suggested that a single injection of SI-613 was effective and that efficacy was higher with 30 mg SI-613 than with 15 mg SI-613. The study also suggested that there were no major safety concerns with either dose of SI-613. Based on the above results, 30 mg was selected as the final clinical dose.

3.3.3. Dosing Regimen and Rationale

The dosing regimen of SI-613 will be repeated IA injections of 30 mg SI-613 administered once every 4 weeks for a total of 3 IA injections at Weeks 0, 4, and 8. In the nonclinical study in antigen-induced rabbit arthritis models, a single IA knee injection of SI-613 significantly inhibited knee joint swelling compared with injections in the control group up to 28 days after the injection. In the repeat-dose phase 2 clinical study in Japanese patients with knee OA, IA knee injections of 30 mg SI-613 at 28-day intervals resulted in statistically significant improvement in pain compared with placebo. Therefore, a 28-day (4-week) dosing interval was selected.

4. **OBJECTIVES**

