7.2.2. Randomization / Visit 2 (Week 0; Day 1)

Visit 2 must occur in a 7- to 14-day window following the Screening visit.

The following procedures will be performed at Visit 2:

- Confirm no use of rescue acetaminophen in the previous 2 days and before the visit at the visit date.
- Review the medical history information.
- Review and update the use of prior and current concomitant medications and concomitant
 therapies, confirming that the subject has not used any prohibited medications or
 therapies and has not changed the dose and/or regimen of restricted medications or
 therapies since the previous visit.
- Collect vital signs.
- Collect urine and perform a dipstick urine pregnancy test.
- Collect the acetaminophen container from the previous visit and count acetaminophen usage.
- Collect the subject daily diary and assess compliance.
- Record AEs.
- Perform examination of the target knee.
- Administer the WOMAC.
- Administer the SF-36.
- Administer the PASE.
- Conduct the 50-foot walk test and measure pain immediately following using a 100-mm VAS.
- Confirm that the subject meets all of the inclusion criteria and none of the exclusion criteria and is therefore eligible for the study.

- Randomize the subject.
- Perform the first injection.
 - The subject will be instructed to avoid any strenuous activities (such as jogging, tennis, and other active sports or heavy lifting) and prolonged weight-bearing activities (such as standing for more than 1 hour) for 48 hours following the IA injection.
- Record AEs that have occurred during the study visit.
- Distribute new subject daily diary.
- Distribute new acetaminophen tablets.

7.2.3. Follow-up Visits 3 (Week 1; Day 8 ± 2), 4 (Week 2; Day 15 ± 2), 6 (Week 6; Day 43 ± 6), 8 (Week 10; Day 71 ± 6), and 10 (Week 18; Day 127 ± 14)

The following procedures will be performed at Visits 3, 4, 6, 8 and 10:

- Confirm no use of rescue acetaminophen in the previous 2 days and before the visit at the visit date.
- Review and update the use of concomitant medications and therapies, confirming that the subject has not used any prohibited medications or therapies and has not changed the dose and/or regimen of restricted medications or therapies since the previous visit.
- Collect vital signs.
- Record AEs.
- Collect the acetaminophen container from the previous visit and count acetaminophen usage.
- Collect the subject daily diary and assess compliance.
- Perform examination of the target knee.

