- Administer the WOMAC.
- Record the PGIC.
- Administer the PASE.
- Record the CGIC.
- Record AEs that have occurred during the study visit.
- Distribute new subject daily diary.
- Distribute new acetaminophen tablets.

7.2.4. Additional Injection Visits 5 (Week 4; Day 29 \pm 7) and 7 (Week 8; Day 57 \pm 7)

The following procedures will be performed at Visits 5 and 7:

- Confirm no use of rescue acetaminophen in the previous 2 days and before the visit at the visit date.
- Review and update the use of concomitant medications and therapies, confirming that the subject has not used any prohibited medications or therapies and has not changed the dose and/or regimen of restricted medications or therapies since the previous visit.

- Collect vital signs.
- Collect urine and perform a dipstick urine pregnancy test.
- Collect urine sample for laboratory tests (qualitative urinalysis regarding glucose, protein and urobilinogen).
- Collect blood sample for laboratory tests (complete blood count and complete metabolic profile).
- Record AEs.
- Collect the acetaminophen container from the previous visit and count acetaminophen usage.
- Collect the subject daily diary and assess compliance.
- Perform examination of the target knee.
- Administer the WOMAC.
- Record the PGIC.
- Administer the SF-36.
- Administer the PASE.
- Record the CGIC.
- Perform the injection.
 - The subject will be instructed to avoid any strenuous activities (such as jogging, tennis, and other active sports or heavy lifting) and prolonged weight-bearing activities (such as standing for more than one hour) for 48 hours following the IA injection.
- Record AEs that have occurred during the study visit.
- Distribute new subject daily diary.
- Distribute new acetaminophen tablets.

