9.2. Rescue Medication

Subjects will be provided with acetaminophen at each clinic visit to use as a rescue medication for breakthrough pain in the target knee, and subjects will be instructed to use the acetaminophen only if the pain in the target knee is of sufficient severity to require use of the rescue medication. No acetaminophen use is permitted from the 2 days before to the end of each study visit. Subjects will be asked to bring the acetaminophen container(s) with any remaining tablets to the next visit.

Temporary use of over-the-counter acetaminophen is allowed for the treatment of other AEs, except for the periods from the 2 days before to the end of each study visit. The use of over-the-counter acetaminophen should be limited to up to 3 days between each visit for Visits 1 through 4, up to 5 days between each visit for Visits 4 through 9, and up to 20 days between each visit for Visit 9 through 11. Subjects should report all over-the-counter acetaminophen use to the investigator at each visit.

Subjects will be advised to limit their total acetaminophen use, from both the study-provided acetaminophen and over-the-counter sources, to 3000 mg/day. Subjects will be required to abstain from all use of acetaminophen from the 2 days before to the end of each study visit.

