13.4.3. Efficacy Analyses

13.4.3.1. Primary Efficacy Analysis

The primary efficacy analysis will be performed on the WOMAC VAS pain subscore using longitudinal analysis to incorporate information from pain scores assessed at Weeks 1, 2, 4, 6, 8, 10, and 12. A direct likelihood approach as implemented in the SAS MIXED procedure will be used to estimate model parameters designed to reflect group-specific mean values over time. The primary efficacy hypothesis concerns the over a 12-week evaluation period from Week 1 to Week 12, and the group comparison is defined as the average effect over assessments during these weeks. Supporting analyses involve comparisons reflecting group differences at the various study visits, including landmark analysis at Week 12 and early onset of efficacy at Week 1. In all cases, model parameters will be used to determine comparisons for which statistical significance against null zero hypotheses and corresponding 95% confidence intervals will be provided. The basic longitudinal model will be specified as a repeated-measures model that expresses the pain score as a linear function of treatment, time, treatment-by-time interaction, and clinically relevant covariates (pretreatment pain measurement, K-L score, and sex) and a fixed-site effect.

The model is designed to account for correlations among responses over time and to use these correlations to implicitly impute missing values from the non-missing values. The type=UN option in the SAS MIXED procedure will be used to model correlation patterns across time.

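### Do injection windows counted from Day 1 undermine the 28-day dosing interval or the Week 6 and Week 10 pain scores?

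*Combined protocol and SAP*

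**What the plan says.** Section 3.3.3 sets injections at Weeks 0, 4 and 8. It relies partly on the repeat-dose phase 2 study, in which "IA knee injections of 30 mg SI-613 at 28-day intervals resulted in statistically significant improvement in pain compared with placebo", and concludes: "Therefore, a 28-day (4-week) dosing interval was selected".

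Section 7.2 and Table 2 turn this into study days. Injection 1 is on Day 1 (Visit 2). Injections 2 and 3 are at Visit 5 (Day 29 ± 7) and Visit 7 (Day 57 ± 7). The Week 6 and Week 10 assessments are Visit 6 (Day 43 ± 6) and Visit 8 (Day 71 ± 6), and Week 12 is Visit 9 (Day 85 ± 7). No section ties a window to the date of the previous injection or states a permitted range between injections.

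The primary model in Section 13.4.3.1 uses "pain scores assessed at Weeks 1, 2, 4, 6, 8, 10, and 12". Section 13.5.3 analyzes data by the visit recorded in the eCRF. Two conduct rules bear on early scores. Subjects avoid strenuous activity and prolonged weight-bearing "for 48 hours following the IA injection" (Sections 7.2.2, 7.2.4 and 8.4), and under Section 9.2 "No acetaminophen use is permitted from the 2 days before to the end of each study visit".

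**The concern.** A reader who sees ± 7 days around a four-week interval will probably infer gaps of 21 to 35 days. That holds between injections 1 and 2, because Day 1 has no window. It does not hold between injections 2 and 3: both dates float independently, so the tolerance on the gap doubles to ± 14 days. The regimen under test is one injection every four weeks, yet a fully compliant subject could have two injections 14 days apart, half the interval that the rationale supports.

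The same windows abut the next assessment (Day 36 then Day 37; Day 64 then Day 65). A Week 6 or Week 10 pain score could therefore be taken the day after an injection, inside the activity restriction, and still enter the primary analysis as an ordinary value. If that were common, two of the seven averaged time points would partly measure the immediate aftermath of the injection.

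**Working it through.** **Inputs.** Visit days and windows from Sections 7.2.2 to 7.2.5 and Table 2; planning difference 7.5 mm, SD 23 mm and 40 per arm from Section 13.1.

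**The plan's own figure.** 29 − 1 = 28 and 57 − 29 = 28. The nominal schedule reproduces the stated interval exactly.

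**Extremes with all visits in window.** Minimum gap = earliest later day − latest earlier day. Maximum gap = latest later day − earliest earlier day.

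| Gap | Nominal | Minimum | Maximum |
|---|---|---|---|
| Injection 1 to 2 | 28 | 22 − 1 = 21 | 36 − 1 = 35 |
| Injection 2 to 3 | 28 | 50 − 36 = 14 | 64 − 22 = 42 |
| Injection 1 to 3 | 56 | 50 − 1 = 49 | 64 − 1 = 63 |
| Injection 2 to Week 6 score | 14 | 37 − 36 = 1 | 49 − 22 = 27 |
| Injection 3 to Week 10 score | 14 | 65 − 64 = 1 | 77 − 50 = 27 |
| Injection 3 to Week 12 score | 28 | 78 − 64 = 14 | 92 − 50 = 42 |

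A 14-day gap between injections 2 and 3 requires injection 2 on Day 36, so it always follows a 35-day gap. The three injections never span fewer than 49 days.

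**How many permitted schedules are extreme.** Injections 2 and 3 have 15 × 15 = 225 in-window day pairs. One gives 14 days and one gives 42. Gaps under 21 days number 7 + 6 + 5 + 4 + 3 + 2 + 1 = 28, and 28 more exceed 35, so 56/225 = 25% lie outside 21 to 35. Injection 2 and Week 6 have 15 × 13 = 195 pairs. One gives a one-day gap and two give a two-day gap, so 3/195 = 1.54% are within two days. Injection 3 and Week 10 give the same counts. These are counts of permitted schedules, not forecasts of how often they will occur.

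**Possible effect on the primary contrast (illustration).** Assume visit days are independent and uniform within their windows. With 80 subjects there are 2 × 80 = 160 Week 6 and Week 10 scores, of which 160 × 0.0154 ≈ 2.5 are within two days of an injection. Assume also that each such score is shifted by 20 mm, and in one arm only. A simple seven-visit average then moves by (2/7) × 0.0154 × 20 ≈ 0.09 mm. If 10% of those scores were affected, the shift would be (2/7) × 0.10 × 20 ≈ 0.6 mm. For comparison, the planning standard error is 23 × √(2/40) = 5.14 mm.

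**What counting from the previous injection would cost.** Purely to show the trade-off, keep the same seven-day tolerance but count injection 3 from injection 2. Injection 3 could then fall from 22 + 21 = Day 43 to 36 + 35 = Day 71. That range overlaps the present Week 6 window (Days 37 to 49) and Week 10 window (Days 65 to 77), so the later assessments would have to move too. Under the present rule the windows for Visits 5 to 9 (Days 22–36, 37–49, 50–64, 65–77, 78–92) do not overlap, and a late injection does not push later visits off schedule.

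**The case for a change.** The best case for acting is that the doubled tolerance is neither stated nor justified anywhere. A quarter of permitted day pairs for injections 2 and 3 lie outside 21 to 35 days, so this is more than a single-cell curiosity. The plan is also uneven: after injection 1 the first score comes no earlier than Day 6, five days later, while after injections 2 and 3 the minimum is one day. A visit in window is not a timing deviation, so nothing would flag a 14-day gap for the per-protocol population. Stating the intended range and running one sensitivity analysis would be cheap.

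The gap in the text is real, and so is the unevenness. The consequences drawn from it are weaker.

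- The 29% (2 of 7) counts visits at which the corner case is possible, not scores affected.
- The activity rule limits strenuous activity and prolonged weight-bearing, with standing for more than an hour as its example. Ordinary walking is not restricted.
- Every injection day is already a visit day under the acetaminophen ban, so a next-day visit adds only the time between the two visits.
- Whether a next-day score reflects only the hours since the injection depends on the WOMAC recall period, which Section 10.1 does not give.
- The documents contain no safety data by injection interval, so a safety effect is neither shown nor excluded. Adverse events, vital signs and the target knee are checked at every visit, and laboratory tests are done at both later injection visits.
- Both arms are injected under the same windows, so a shared reaction to the procedure adds noise rather than bias. A reaction specific to one product could differ between arms, and the illustration allows for that.
- A sensitivity analysis that dropped two or three scores of 160 could not alter a conclusion.

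**Conclusion.** No change is needed. The windows permit 14 to 42 days between injections 2 and 3 and, rarely, a pain score one or two days after an injection. They do so as a tolerance around a nominal schedule of exactly 28 days, so the stated interval and the windows do not conflict. Counting from Day 1 lets individual gaps vary in exchange for assessments that stay aligned to Weeks 1 to 12 and do not overlap, which is a reasonable choice for an endpoint averaged over that period.

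The likely effect on the primary contrast is about 0.09 mm, or about 0.6 mm if one in ten Week 6 and Week 10 scores were affected, against a planning difference of 7.5 mm and a standard error of 5.14 mm. This rests on uniform, independent visit days and an assumed one-sided 20 mm shift. The documents do not show how visits will actually cluster.

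Analysts who want to describe the spread can derive days since the last injection from recorded dates without any change to the plan. Whether any between-injection spacing matters clinically is for the sponsor's clinical team, and nothing here suggests a different interval.
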